#### 9.4.4 PGA

PGA consists of a single question, “Considering all the ways that your heart condition affects you, what is your assessment of how much your heart condition is impacting your life today?” Possible responses are “no impact,” “mild impact,” “moderate impact,” and “severe impact.” PGA will be listed and summarized. The summary table will include p-values for treatment group comparison of improvement or no change from baseline vs. worsening from baseline, analyzed using generalized estimating equations with the sandwich variance estimator for correlated (longitudinal) data.

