2.3 Secondary Objectives

The secondary safety objective is to compare the safety profiles of CAP-1002 and placebo over 12 months based on pre-specified clinical events and development of increased HLA antibody levels.

The secondary efficacy objective is to evaluate whether administration of CAP-1002 by intracoronary infusion may result in other left ventricular structural or functional cardiac benefits for subjects with ischemic left ventricular dysfunction and a previous MI. Also evaluations will investigate whether administration of CAP-1002 may result in clinical or biomarker benefits for subjects with ischemic left ventricular dysfunction and a previous MI.

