6.11 Clinical Function and Quality of Life Measures

At the screening, 6 month and 12 month study visits, the subject will be asked to complete the Minnesota Living with Heart Failure Questionnaire (MLHFQ), the Short Form-36 health survey (SF-36), the Work Productivity and Activity Impairment Questionnaire: Specific Health Problem (WPAI:SHP), and to make a global assessment of the improvement or worsening of his/her condition (Patient Global Assessment).

In addition, subjects will perform a Six Minute Walk test at screening, and at the 6 and 12 month study visits. New York Heart Association (NYHA) functional status will be evaluated at screening, 1 month, 3 months, 6 months and 12 months study visits.

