9.6.2 Secondary Efficacy

All comparisons in the secondary analyses will be based on a null hypothesis of no difference in the endpoint between subjects administered CAP-1002 as compared to placebo and an alternate hypothesis of a difference in the endpoint for subjects administered CAP-1002 as compared to placebo. Secondary analyses will be based on a random effects model similar to the primary but will be based on an alpha of 0.05 without controlling for multiplicity.

The following secondary efficacy endpoints will be evaluated during the six-month and twelve-month follow-up periods:

Global LV Function measures

1. Percent change and change from baseline in MRI assessment of LVEF
2. Percent change and change from baseline in MRI assessment of left ventricular end-diastolic and end-systolic volumes indexed to BSA

Structural measures

3. Change from baseline in MRI assessment of infarct size as a percent of left ventricular mass
4. Percent change and change from baseline in MRI assessment of infarct size expressed in grams
5. Percent change and change from baseline in MRI assessment of viable mass expressed in grams

Regional measure

6. Percent change and change from baseline in MRI assessment of function in the region which received CAP-1002 therapy

Clinical function/status measures

7. Changes from baseline in distance covered in six minute walk test

8. Change from baseline in Minnesota Living with Heart Failure Questionnaire (MLHFQ) score
9. Change from baseline in SF-36 score
10. Change from baseline in WPAI:SPH score
11. Change from baseline in Patient Global Assessment (PGA) score
12. Change from baseline in NYHA Class

Biomarker

13. Percent change and change from baseline in NT-proBNP
14. Change from baseline in log transformed NT-proBNP

Additional detail regarding secondary endpoint analyses can be found in the SAP.

Analyses of the secondary efficacy endpoints will be performed using the same longitudinal modeling approach as the primary efficacy endpoint; the baseline covariate used in the model will be the baseline of the endpoint being analyzed. Two-sided testing will be performed at level $p=0.05$.

A correlational analysis will be presented (for tissue based and functional measures) with Pearson's correlation coefficient for all possible pairs of efficacy endpoints and where appropriate the Spearman's correlation coefficient will be presented.

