### 2.3.6 Secondary Efficacy Endpoints

The following secondary efficacy endpoints will be evaluated at 6 and 12 months post IP administration unless otherwise noted:

1. Absolute and relative change from baseline in global LV function measures:
  - a) MRI assessment of LV ejection fraction (LVEF)
  - b) MRI assessment of LV end diastolic volume (LVEDV) and end systolic volume (LVESV) indexed to body surface area (BSA)
2. Absolute and relative change from baseline in structural measures:
  - a) MRI assessment of infarct size as a percent of LV mass
  - b) MRI assessment of infarct size expressed in grams
  - c) MRI assessment of viable mass expressed in grams
  - d) MRI assessment of scar transmurality
3. Absolute and relative change from baseline in regional measures:

- a) MRI assessment of function and structure by segment or groups of segments (e.g., region which received the IP)
- 4. Absolute change from baseline in clinical function/status measures:
  - a) Distance covered in six minute walk test (6MWT)
  - b) Minnesota Living with Heart Failure Questionnaire (MLHFQ) score
  - c) Patient Global Assessment (PGA) score
- 5. Absolute and relative change from baseline in cardiac biomarkers:
  - a) NT-proBNP

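### The only formal test of the Patient Global Assessment (PGA) pools improved with unchanged subjects, and so does not match the endpoint both documents define as a change in score

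*SAP*

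**What the plan says.** SAP 9.4.4 describes the PGA as a single question with four ordered answers, from no impact to severe impact of the heart condition on the subject's life. It plans descriptive output ("PGA will be listed and summarized") and one inferential comparison, the "comparison of improvement or no change from baseline vs. worsening from baseline". The method for this binary outcome is GEE with a robust variance for repeated measurements. It names no other PGA test.

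The endpoint is defined differently elsewhere:

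- Protocol 9.6.2 lists it as "Change from baseline in Patient Global Assessment (PGA) score".
- SAP 2.3.6 places "Patient Global Assessment (PGA) score" under absolute change from baseline in clinical function and status measures.

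Protocol 9.6.2 also fixes the method: "Analyses of the secondary efficacy endpoints will be performed using the same longitudinal modeling approach as the primary efficacy endpoint", with the endpoint's own baseline as covariate and two-sided testing at 0.05. SAP Section 9 likewise models changes from baseline with the baseline value as covariate. SAP Section 14 gives the deviations from the protocol's statistical methods as none.

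**The concern.** The endpoint is a change that can go either way on an ordered scale, and Protocol 6.11 describes the PGA as recording both improvement and worsening. The planned test keeps only one boundary of that change: worse, or not worse. A subject who moves from severe to mild impact counts the same as one who stays at severe. A subject at the severe level at baseline cannot worsen, and so counts as favourable whatever happens.

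At stake is whether the reported PGA p-value answers the question the endpoint poses. If CAP-1002 made patients feel better without changing how many feel worse, the PGA p-value would carry no information about it. A reader of the results table could take the non-significant result as evidence of no effect on the PGA.

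The SAP also treats comparable measures differently without giving a reason. NYHA class, another ordered scale, is compared on the distribution of change (SAP 9.3). The MLHFQ, SF-36 and WPAI scores are tested on change from baseline (SAP 9.4.1 to 9.4.3).

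**Working it through.** **1. What the coding implies.** Let Y = 1 if the subject has worsened and Y = 0 if improved or unchanged. Write w, s and i for the proportions worse, same and improved, with w + s + i = 1. The test compares P(Y = 1) = w between arms. Moving a proportion d from same to improved gives (w, s − d, i + d), and w is unchanged. The tested quantity therefore does not depend on d. This needs no assumed rate, and it holds for the two-visit GEE as well as for a single-visit test.

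**2. Plan figures available.** The documents give no rate, effect size or power for the PGA, so there is no PGA figure to reproduce. The stated power of more than 90% at a total of 100 subjects concerns the MRI primary endpoint only. Protocol 3.1 gives 93 completers at 2:1, hence 93 × 2/3 = 62 on CAP-1002 and 93 × 1/3 = 31 on placebo. Secondary tests are two-sided at 0.05.

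**3. Size under assumed rates.** Trials were simulated at one visit. The split was tested by Fisher's exact test (lower figure) and by a z-test (upper figure). The ordinal test is a rank-sum test on worse / same / improved. All PGA rates are assumptions.

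| Improved/same/worse, CAP-1002 v placebo | Split | Ordinal |
|---|---|---|
| 45/45/10% v 20/65/15% | 8-12% | about 60% |
| 45/45/10% v 20/70/10% (equal worsening) | 3-4% | 52% |
| 30/60/10% v 20/65/15% (modest effect) | 8-12% | 19% |
| 20/75/5% v 20/55/25% (only less worsening) | 73-80% | 37% |

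**4. Hand check of the split (z-test).** Power ≈ Φ((|d| − 1.96·SE0)/SE1), plus the small opposite tail. Here d is the difference in worsening, SE0 the pooled and SE1 the unpooled standard error.

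- Row 1: d = 0.05. Pooled rate = (62 × 0.10 + 31 × 0.15)/93 = 10.85/93 = 0.1167. SE0 = √(0.1167 × 0.8833 × (1/62 + 1/31)) = 0.0706. SE1 = √(0.10 × 0.90/62 + 0.15 × 0.85/31) = 0.0746. Power ≈ Φ((0.05 − 0.1384)/0.0746) = Φ(−1.19) = 0.118; with the opposite tail of 0.006, 12%.
- Row 2: d = 0, so power is the type I error rate, nominally 5% and lower with Fisher's test.
- Row 4: d = 0.20. The pooled rate is again (3.1 + 7.75)/93 = 0.1167, so SE0 = 0.0706. SE1 = √(0.05 × 0.95/62 + 0.25 × 0.75/31) = 0.0826. Power ≈ Φ((0.20 − 0.1384)/0.0826) = Φ(0.75) = 77%.

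These agree with the simulated figures.

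**5. Wider ranges, also assumed.** With equal worsening of 10-20%, 25-35% improved on placebo and 20 to 30 points more improved on CAP-1002, the z-test split rejects in about 4-5% of trials and the ordinal test in about 27-67%. If both boundaries shift by a common odds ratio of 2 to 4 (placebo 30% improved, 10-20% worse), the split has about 14-54% power and the ordinal test about 35-90%.

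**The case against.** The strongest defence is that avoiding decline is a legitimate goal. The secondary objective asks "whether administration of CAP-1002 may result in clinical or biomarker benefits", and fewer subjects worsening is a clinical benefit. Protocol 7.7 presents remodeling markers as surrogates for disease progression. A binary split is a recognised choice for a four-level item, and GEE with a sandwich variance suits repeated binary data. A linear model on a four-level score has drawbacks of its own, so some departure from the protocol's model is reasonable. Row 4 shows that if the benefit is purely less worsening, the split is the better test. All of this stands. What it does not supply is an endpoint definition: neither document defines the PGA endpoint as worsening, and the change of method is not declared.

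Three further objections also stand. The power figures rest on rates the documents do not contain, and the ranking depends on the pattern of effect. The simulations use one visit and simple tests, so they are not the power of the planned GEE, although step 1 applies to it unchanged. The boundary problem has a mirror image: subjects at no impact cannot improve, which costs an ordinal change analysis power, and the baseline distribution is not given.

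A reader might infer that improvement on the PGA cannot be detected at all. The documents do not support this. The PGA is listed and summarised by visit window, and a PGA figure is planned (SAP 7.2.1 and Appendix C), so improvement would be visible there; only the p-value ignores it. Nor do they support the inference that CAP-1002 is expected to act on the PGA through improvement alone.

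**Conclusion.** The concern holds in limited form. By its coding, the one formal PGA test cannot register a shift from unchanged to improved. That does not match the change-in-score endpoint in Protocol 9.6.2 and SAP 2.3.6, or the protocol's longitudinal analysis of secondary endpoints, and SAP Section 14 does not record the difference. These points rest on the text alone.

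The size is conditional. Under the assumed rates, the split loses most of the available power when benefit appears mainly as improvement, and it gains when benefit appears only as less worsening. An ordinal test is preferable because it matches the defined endpoint and responds to movement in both directions, not because it always has more power.

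The consequence is small. The PGA is one of several secondary endpoints tested at 0.05 without multiplicity control, other patient-reported measures are tested on change from baseline, and the primary analysis is unaffected.

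**What to change.** - Make the main PGA test an analysis of the four-level response or its change: a longitudinal proportional-odds model over Months 6 and 12 with baseline level as covariate, or a rank test of change at each visit that accounts for baseline level.
- Keep the worsened proportion, with the GEE already specified, as a supplementary summary, and show improved, unchanged and worsened counts by arm and visit.
- Reconcile SAP 9.4.4 with SAP 2.3.6 and Protocol 9.6.2, and record in SAP Section 14 any remaining departure from the protocol's model. If worsening is the intended target, define the endpoint that way in both documents.

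This is a free improvement: same data, same visits, standard software, and a short SAP edit. It should be made before the Month 6 administrative analysis unblinds sponsor staff to efficacy data.

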## 9.5 NT-proBNP

Observed, absolute change from baseline, and percent change from baseline in NT-proBNP will be listed and summarized. Summary tables will include p-values for treatment group comparisons of changes from baseline.

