The secondary efficacy objective is to evaluate whether administration of CAP-1002 by intracoronary infusion may result in other left ventricular structural or functional cardiac benefits for subjects with ischemic left ventricular dysfunction and a previous MI. Also evaluations will investigate whether administration of CAP-1002 may result in clinical or biomarker benefits for subjects with ischemic left ventricular dysfunction and a previous MI.

Study Design:

In Phase 2, the Primary Randomized Cohort will enroll up to approximately 103 subjects with a previous myocardial infarction (MI) and resultant ischemic left ventricular dysfunction meeting all inclusion and no exclusion criteria. The Primary Randomized Cohort will include the Recent and Chronic MI strata (n= approximately 51-52 per stratum). These 103 subjects will be randomized in a double-blind fashion to receive either CAP-1002 or placebo (collectively referred to as Investigational Product [IP]) in a 2:1 ratio favoring CAP-1002 to achieve up to 93 subjects with complete 12 month data (assumes 10% non-completion rate and 103 subjects randomized). After completion of the screening procedures and meeting all inclusion and exclusion criteria, study subjects will be randomized to receive CAP-1002 or placebo administered via intracoronary infusion. All subjects in the Primary Randomized Cohort will be followed at week 2 and at months 1, 3, 6 and 12 after planned CAP-1002 or placebo infusion. Efficacy will be assessed at all specified post-infusion visits, with the 12 month visit being the primary efficacy endpoint. An administrative interim analysis of the final 6 month data will be performed when all subjects in the Primary Randomized Cohort have completed the 6 month visit to assist in planning Phase III studies.

The double-blind, placebo-controlled design of the Primary Randomized Cohort will maximize

the study's ability to assess both safety and efficacy, as both may be subject to bias from the perspective of Investigators and subjects.

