2.4.1 Efficacy Assessments

The primary efficacy endpoint is the percent change from baseline in MRI assessment of infarct size as a percent of left ventricular mass 12 months after administration of treatment (either CAP-1002 or placebo). The following will be evaluated as secondary efficacy endpoints during the six-month and twelve-month follow-up periods:

Global LV Function Measures

1. Percent change and change from baseline in MRI assessment of LVEF
2. Percent change and change from baseline in MRI assessment of left ventricular end-diastolic and end-systolic volumes indexed to BSA

Structural measures

3. Change from baseline in MRI assessment of infarct size as a percent of left ventricular mass
4. Percent change and change from baseline in MRI assessment of infarct size expressed in grams
5. Percent change and change from baseline in MRI assessment of viable mass expressed in grams

Regional measure

6. Percent change and change from baseline in MRI assessment of function in the region which received CAP-1002 therapy

Clinical function/status measures

7. Percent change and change from baseline in distance covered in six minute walk test
8. Change from baseline in Minnesota Living with Heart Failure Questionnaire (MLHFQ) scores (Total score, Physical Dimension score, and Emotional Dimension score)
9. Change from baseline in Patient Global Assessment (PGA) score

Biomarker

10. Percent change and change from baseline in NT-proBNP
11. Change from baseline in log transformed NT-proBNP

Additional detail regarding secondary endpoint analyses can be found in the SAP.

[figure not shown]

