## 7.3 Data Analysis

- The reference date used for summaries and analyses will depend on the analysis population, as follows:
  - ITT population: randomization date
  - mITT population: IP administration date
  - Safety population: IP administration date
  - Per protocol population: IP administration date
- Categorical variables will be summarized as frequencies and percentages in each category. Percentages will be reported to one decimal place. Unless otherwise noted in Sections 8-10, categorical variables will be analyzed using chi square tests of association or, if any contingency table cell has less than 5 subjects, Fisher's exact test.
- Continuous variables will be summarized by numbers of subjects, means, standard deviations, medians, and ranges. The number of decimal places for minimums and maximums will be the same as the original data. The number of decimal places for means, medians, and interquartile ranges will be the same as the original data plus one. The number of decimal places for measures of variance will be the same as the original data plus two. Unless otherwise noted in Sections 8-10, continuous variables will be analyzed using t-tests. Non-parametric tests and data transformations will be considered for variables with distributions that violate t-test assumptions.
- Data with qualifiers (e.g., “<”) will be listed with but summarized without the qualifier.
- P-values will be presented to two decimal places if  $> 0.01$ , to three places if  $< 0.01$  but  $> 0.001$ , and to four places if  $< 0.001$  but  $> 0.0001$ . P-values  $< 0.0001$  will be presented as “ $< 0.0001$ .”
- Statistical tests will be two-sided and tested at the 0.05 significance level unless otherwise noted in Sections 8-10.
- It is understood that statistical non-significance is not an indicator of equivalence.

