## 9. EFFICACY ANALYSIS

All efficacy parameters will be listed for the primary ITT population and summarized for the mITT population. The primary analysis of primary and secondary efficacy endpoints will be done using the primary mITT population. Secondary analyses may be done using the other analysis populations defined in [Section 6](#) or in subgroups defined in [Section 7.4](#). In addition, “last observation” analyses will be done for certain parameters for which some subjects’ final assessments were done too late to be included in the Month 12 analysis window.

Analyses of changes from baseline will be done using general linear models with baseline values as covariates. Analyses of the effect of treatment group, analysis window (e.g., baseline, Month 6, Month 12), and their interaction will be done using mixed effects linear regression, with subject as a random effect, analysis window, and treatment group as fixed effects, and baseline as a fixed-effect covariate. For “last observation” analyses, “time” as a continuous covariate will be substituted for analysis window. Study site may also be included as a random effect if there is evidence of correlation within study sites (per the interclass correlation coefficient from the unconditional model) and/or if doing so appreciably improves the model fit (e.g., per Akaike’s Information Criterion). Other covariates that may be considered include age (< 65 vs.  $\geq$  65 years), sex, race (African-American vs. other), baseline 6MWT, baseline LVESV, baseline NT-proBNP, and DSA (as an indicator variable). Residuals will be evaluated for substantial departure from normality and independent and constant variance and appropriate remedies (e.g., data transformations, detecting and assessing the influence of outliers, alternative analytical approaches) will be attempted when necessary. An unstructured covariance will be the default covariance structure but other structures (e.g., compound symmetry) may be used to evaluate sensitivity to the choice of structure or, if study site is included as a random effect, to achieve convergence.

Assuming missing observations are “missing at random” (MAR), i.e., the fact that they are missing is unrelated to the missing variable but can be related to another variable on which data have been collected, the maximum likelihood (ML) approach is able to handle subjects with

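### The SAP does not carry over the protocol's log-transformed NT-proBNP endpoint and records no deviation, so the log scale survives only as a conditional remedy

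*SAP*

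**What the plan says.** **Protocol.** The synopsis (item 11), section 2.4.1 (item 11) and section 9.6.2 (item 14) each list "Change from baseline in log transformed NT-proBNP" as a numbered secondary efficacy endpoint. In each list it follows a separate item for percent change and change in NT-proBNP. Section 9.6.2 applies the primary endpoint's longitudinal modelling approach to the secondary endpoints and specifies that "the baseline covariate used in the model will be the baseline of the endpoint being analyzed". Testing is two-sided and "will be based on an alpha of 0.05 without controlling for multiplicity".

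**SAP.** Section 2.3.6 places NT-proBNP under "Absolute and relative change from baseline in cardiac biomarkers" and names no log-scale version. Section 9.5 says "Observed, absolute change from baseline, and percent change from baseline in NT-proBNP will be listed and summarized", with p-values for the treatment comparisons of those changes. No log-scale NT-proBNP analysis is named anywhere in the SAP.

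Two general clauses mention transformations. Section 9, after saying that residuals will be evaluated, adds that "appropriate remedies (e.g., data transformations, detecting and assessing the influence of outliers, alternative analytical approaches) will be attempted when necessary". Section 7.3 says "Non-parametric tests and data transformations will be considered for variables with distributions that violate t-test assumptions".

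Section 14, on deviations from the protocol's statistical methods, reports none.

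**The concern.** The protocol commits to three NT-proBNP measures: absolute change, percent change and change on the log scale. The SAP carries two of them forward. The third is neither kept nor listed as removed, although the protocol refers to the SAP for further detail on its secondary analyses.

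Two things are at stake. The first is pre-specification. A scale that the protocol fixed before the data would be used only if someone judges the residuals unsatisfactory, with no stated criterion. The endpoint is tested at 0.05 without multiplicity control, so a scale chosen after inspection makes a positive result harder to interpret.

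The second is sensitivity. If NT-proBNP is right-skewed and treatment acts proportionally, a few large values dominate absolute change and, to a lesser extent, percent change. A real effect is then easier to miss on those scales.

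**Working it through.** **Step 1. Endpoint lists compared.**

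| Measure | Protocol synopsis, 2.4.1, 9.6.2 | SAP 2.3.6 | SAP 9.5 |
|---|---|---|---|
| Absolute change | listed | listed | listed, p-value |
| Percent (relative) change | listed | listed | listed, p-value |
| Change in log NT-proBNP | listed, all three places | absent | absent |

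Against the supplied protocol, the entry in SAP section 14 is therefore incomplete.

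**Step 2. What the transformation clauses secure.** Both are general. Neither names NT-proBNP, fixes the log scale or sets a numeric trigger. They permit a log analysis without committing to one.

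**Step 3. Size of the possible power loss.** The documents give no SD, skewness, expected effect or power for NT-proBNP, so there is no figure of theirs to reproduce. What follows is illustrative.

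Inputs from the documents: "2:1 ratio favoring CAP-1002 to achieve up to 93 subjects with complete 12 month data" (Protocol synopsis), taken as 62 versus 31; two-sided alpha 0.05; the baseline of the analysed endpoint as covariate.

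Assumed inputs: log-normal NT-proBNP; log SD σ from 0.5 to 1.2 at both times; log-scale correlation ρ of 0.6 or 0.8 between baseline and follow-up; a multiplicative effect sized to give log-scale ANCOVA about 80% power:

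- SE of the log difference = σ × √(1 − ρ²) × √(1/62 + 1/31)
- true ratio = exp(−2.85 × SE)

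Example, σ = 1.0 and ρ = 0.6: SE = 1.0 × 0.8 × 0.220 = 0.176, so the ratio = exp(−0.50) = 0.606.

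Results from 2,500 simulated trials per row, using ANCOVA on each scale. The absolute and percent analyses use untransformed baseline, the log analysis uses log baseline, and only rejections favouring CAP-1002 are counted. Losses are in percentage points.

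| σ | ρ | True ratio | Log | Absolute | Percent | Loss, absolute | Loss, percent |
|---|---|---|---|---|---|---|---|
| 0.5 | 0.6 | 0.778 | 79.9% | 75.1% | 74.3% | 4.8 | 5.6 |
| 0.5 | 0.8 | 0.829 | 79.9% | 72.6% | 77.6% | 7.3 | 2.3 |
| 0.8 | 0.6 | 0.669 | 81.3% | 66.8% | 69.5% | 14.5 | 11.8 |
| 0.8 | 0.8 | 0.740 | 81.2% | 63.2% | 76.3% | 18.0 | 4.9 |
| 1.0 | 0.6 | 0.606 | 82.0% | 61.6% | 64.7% | 20.4 | 17.3 |
| 1.0 | 0.8 | 0.686 | 79.4% | 56.6% | 73.7% | 22.8 | 5.7 |
| 1.2 | 0.6 | 0.548 | 81.1% | 54.5% | 59.4% | 26.6 | 21.7 |
| 1.2 | 0.8 | 0.637 | 79.9% | 47.4% | 69.4% | 32.5 | 10.5 |

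With no effect (ρ = 0.8, each σ), rejections favouring CAP-1002 were 2.2% to 2.8% on all three scales, against a nominal 2.5%. The difference is one of power, not of type I error.

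**Step 4. Other assumptions.** With baseline log SD 1.0, SD of log change 0.7 and a true ratio of 0.65, power was about 78% (log), 72% (percent) and 47% (absolute). With SD of log change 0.8 it was about 68%, 59% and 39%. At a weaker ratio of 0.80, percent change lost only about 1 to 2 points to the log scale.

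**The case against.** The strongest reply is that the SAP does not exclude a log analysis. Section 9 covers all efficacy models, says residuals will be evaluated, and names data transformations first among its remedies. In the Step 4 scenario with a ratio of 0.65, ANCOVA residuals failed a Shapiro-Wilk test at 0.05 in over 99% of simulated trials on both the absolute and percent scales. The skewness that costs power is thus the kind of departure such a check would probably find. The SAP is also a supplement to the protocol and nowhere revokes the endpoint. This stands in part: a reader might infer that the SAP permits only raw and percent change, and that is not so. But the SAP specifies no such test or threshold and does not say that the remedy would be a log transformation. A possible remedy is not a pre-specified endpoint.

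Second, the power figures come from a model that favours the log scale by construction, and from a single-time-point ANCOVA instead of the planned longitudinal mixed model. That stands. A reader might infer that the trial has been shown to lose power on NT-proBNP; the documents do not support this, because they give no NT-proBNP distribution. An additive effect could change the comparison.

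Third, the SAP preface cites protocol Amendment 8.1 of 22 February 2017, while the supplied synopsis gives 15 January 2015 as its latest amendment date. The closed-testing text and sample-size assumptions in the two documents match, but identity of versions cannot be confirmed. The mismatch is therefore stated against the supplied protocol.

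**Conclusion.** The point holds as a minor inconsistency between protocol and SAP. A log-scale endpoint listed three times in the protocol is missing from SAP sections 2.3.6 and 9.5, and section 14 does not say so. The choice of scale is left to a conditional, unquantified remedy.

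The illustrative cost, about 5 to 33 points of power against absolute change and 2 to 22 against percent change, depends on a log-normal marker, a multiplicative effect and the assumed SDs and correlations. In most of these scenarios it is smaller for percent change, which the SAP keeps. NT-proBNP is a secondary endpoint outside the closed test, so neither the primary conclusion nor the rule for declaring success depends on it.

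A reader might also infer that log change should become the main NT-proBNP analysis and that absolute and percent change should be only descriptive. The documents do not support that: the protocol does not rank the measures, and its section 9.6.2 has them tested as secondary endpoints. Demoting them would create a new departure.

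**What to change.** Add change from baseline in ln(NT-proBNP) to SAP sections 2.3.6 and 9.5. Analyse it with the same longitudinal model, using ln baseline as covariate in line with Protocol section 9.6.2, and report the back-transformed treatment effect as a geometric mean ratio with a 95% CI. Keep the tests of absolute and percent change beside it.

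If the omission was intended, state the removal and its reason in SAP section 14 instead. Either change should be made before unblinded efficacy data are available to anyone who can influence the analysis; SAP section 5 foresees such access for some sponsor and partner personnel from the administrative interim analyses.

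The cost is a few lines of SAP text and one more model run on data already collected. No visits, samples or subjects are added.
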